---

## LIST OF ABBREVIATIONS

AE	adverse event
AED	antiepileptic drug
ALT	Alanine aminotransferase
ALP	Alkaline Phosphatase
AST	Aspartate aminotransferase
BMI	body mass index
BCR	borderline or clinical range
BRIEF ®	Behavior Rating Inventory of Executive Function ®
BRIEF ® -P	Behavior Rating Inventory of Executive Function ® - Preschool Version
C-SSRS	Columbia-Suicide Severity Rating Scale
CBCL	Child Behavior Checklist
COVID-19	coronavirus disease 2019
DBP	diastolic blood pressure
DEM	Data Evaluation Meeting
ECG	electrocardiogram
eCRF	electronic Case Report Form
ER	emergency room
ETV	Early Termination Visit
FAS	Full Analysis Set
GGT	gamma-glutamyl transpeptidase
HRQoL	health-related quality of life
ILAE	International League Against Epilepsy
LCM	Lacosamide

---

LFT	liver function test
MA	markedly abnormal
MedDRA	Medical Dictionary for Regulatory Activities
PDILI	Potential Drug Induced Liver Injury
PedsQL	Pediatric Quality of Life Inventory
PT	preferred term
SAE	serious adverse event
SAP	Statistical Analysis Plan
SBP	systolic blood pressure
SD	standard deviation
SOC	system organ class
SS	Safety Set
TEAE	treatment-emergent adverse event
TEMA	treatment-emergent markedly abnormal
ULN	upper limit of normal
VNS	vagus nerve stimulation
WHODD	World Health Organization Drug Dictionary

## 1 INTRODUCTION

This Statistical Analysis Plan (SAP) defines the scope of statistical analyses and provides a detailed description of statistical methodology for the statistical analyses to support the final clinical study report for EP0034.

## 2 PROTOCOL SUMMARY

### 2.1 Study objectives

#### 2.1.1 Primary objective

- To assess the long-term safety and tolerability of Lacosamide (LCM) in pediatric subjects

#### 2.1.2 Secondary objective

- To assess the efficacy of LCM during long-term exposure in pediatric subjects

#### 2.1.3 Other objectives

- To assess behavior, cognition, quality of life, and development during long-term LCM exposure in pediatric subjects

### 2.2 Study variables

#### 2.2.1 Primary Safety variables

The primary safety variables include the following:

- Incidence of TEAEs
- Incidence of serious TEAEs
- Incidence of TEAEs leading to study discontinuation

#### 2.2.2 Other safety variables

The other safety variables include the following:

- Safety laboratory tests (hematology; biochemistry including hepatic monitoring of alanine aminotransferase [ALT], aspartate aminotransferase [AST], alkaline phosphatase [ALP], total bilirubin, and gamma-glutamyl transferase [GGT]; endocrinology for all subjects; and urinalysis for subjects  $\geq 5$  years of age)
- Electrocardiograms (ECGs)
- Physical (Tanner Stage, if applicable depending on subject's developmental status) and neurological examinations
- Vital signs (blood pressure and pulse rate)
- Body weight and height

- Change from Baseline in the Achenbach Child Behavior Checklist (CBCL) score: the Achenbach CBCL/1½-5 for children from 1.5 to 5 years of age and the Achenbach CBCL/6-18 for children  $\geq 6$  years of age
- Change from Baseline in the Behavior Rating Inventory of Executive Function – Preschool Version (BRIEF-P) score for subjects  $\geq 2$  and  $< 5$  years of age
- Change from Baseline in the Behavior Rating Inventory of Executive Function (BRIEF) score for subjects  $\geq 5$  years of age
- Change from Baseline in the Bayley-III scales in subjects  $< 18$  months of age at study entry (applicable only to subjects enrolled in English-speaking countries)

## 2.2.3 Efficacy variables

### 2.2.3.1 Primary efficacy variables

No primary efficacy variables are defined for this study.

### 2.2.3.2 Secondary efficacy variables

The secondary efficacy variable planned for analysis will be based on seizure diary data from EP0034 and will include the following for all subjects:

- Percentage of seizure-free days during the study (presented for the overall Treatment Period only)

### 2.2.3.3 Other efficacy variables

The following other efficacy variables will be computed for subjects from SP0969:

- Percentage of 50% responders (subjects with at least a 50% reduction in total partial-onset seizure frequency per 28 days compared to Baseline), with Baseline defined as the period before receiving LCM in the previous pediatric study
- Percentage of 50% responders per seizure type (simple partial, complex partial, or secondarily generalized) compared with Baseline
- Percentage of 75% responders (subjects with at least a 75% reduction in total partial-onset seizure frequency per 28 days compared to Baseline), with Baseline defined as the period before receiving study medication in the previous pediatric study
- Percentage of 75% responders per seizure type (simple partial, complex partial, or secondarily generalized) compared with Baseline
- Absolute and percent reduction in total partial-onset seizures and per partial-onset seizure type (simple partial, complex partial, or secondarily generalized) compared to Baseline
- Partial-onset seizure frequency per 28 days

The following other efficacy variables will be computed for all subjects in EP0034:

- Achievement of seizure-free status (no seizure) during the study for total partial-onset seizure and per seizure type (simple partial, complex partial, or secondarily generalized)

- Clinical Global Impression of Change
- Caregiver's Global Impression of Change
- Change from Baseline in Pediatric Quality of Life Inventory (PedsQL)
- Health care resource use: concomitant medications, medical procedures, health care provider consultations not foreseen by the protocol, and hospital stays

## 2.3 Study design and conduct

This is a Phase 3, multicenter, open-label, extension study to obtain long-term safety and efficacy data in pediatric subjects with epilepsy with partial-onset seizures treated with LCM oral solution or LCM tablets as adjunctive therapy.

Subjects who have participated in SP0967 or SP0969, meet the eligibility requirements of this open-label extension study, and who consent or whose legal representative consents to participation can enroll into EP0034 for a maximum duration of approximately 2 years. The subject's eligibility for the study will be determined at Visit 1 (Week 0).

During the study, LCM will be available in either the oral solution formulation or tablet formulation. Subjects who are able and willing to swallow tablets may be dispensed LCM tablets during the Treatment Period, based on clinical judgment, regardless of their weight.

Approximately 500 subjects from SP0967 and SP0969 may be eligible to enroll in this open-label extension study. The number of sites is dependent on the number of enrolling centers from SP0967 and SP0969.

### Treatment Period

After completion of the Transition Period in the previous pediatric study, subjects will have been transitioned to a dose of LCM according to their weight. Subjects will receive LCM 10mg/kg/day (oral solution) for subjects weighing <30kg, LCM 6mg/kg/day (oral solution) for subjects weighing  $\geq$ 30kg to <50kg, and LCM 300mg/day (tablets) for subjects weighing  $\geq$ 50kg during at least their first week in the Treatment Period of EP0034. After 1 week in EP0034, the investigator may adjust the LCM dose during the Treatment Period (see Table 7-1 in the protocol). Subjects may take either oral solution or tablets during the Treatment Period, based on clinical judgment, regardless of their weight.

Investigators will be allowed to increase or decrease the dose of LCM to optimize tolerability and seizure reduction in each subject. LCM doses may be increased up to a maximum of LCM 600mg/day or 12mg/kg/day, whichever is lower based on body weight; LCM doses may be decreased to a minimum of LCM 100mg/day (tablet) or 2mg/kg/day (oral solution).

During the Treatment Period, study visits are scheduled at Weeks 0, 4, 8, 12, 20, 28, 36, 44, 52, 60, 72, 84, and 96. Telephone contacts are scheduled at Weeks 2, 6, 10, 16, 24, 32, 40, 48, 56, 66, and 78.

At the completion of the study, investigators should discuss treatment options with the subject and/or their legal representative(s) to best manage the subject's epilepsy. Taper of LCM may not be required for some subjects who complete the study, depending on the treatment option selected by the investigator in consultation with the subject and/or legal representative(s). These subjects should complete Visit 13/Termination Visit and then complete the Safety Follow-Up Telephone Contact 30 days (-1/+3 days) after the last dose of LCM. The Safety Follow-Up Visit is not required for subjects

who complete the study and who do not undergo taper of LCM. The Safety Follow-Up Visit and the Safety Follow-Up Telephone Contact are not required for subjects who participate in EP0151 or EP0152.

Subjects who complete the study and discontinue use of LCM (as determined by the investigator in consultation with the subject and/or legal representative) should taper LCM gradually. These subjects should complete Visit 13/Termination Visit and enter the Taper Period.

Subjects who prematurely discontinue the study should complete an Early Termination Visit (ETV). At the time of withdrawal from the study, investigators should discuss treatment options with the subject and/or their legal representative(s) to best manage the subject's epilepsy. Taper of LCM may not be required for some subjects who withdraw from the study prematurely, depending on the treatment option selected by the investigator in consultation with the subject and/or legal representative(s). These subjects should complete the Safety Follow-Up Telephone Contact 30 days (-1/+3 days) after the last dose of LCM.

Subjects who withdraw from the study prematurely and discontinue use of LCM (as determined by the investigator in consultation with the subject and/or legal representative) should taper LCM gradually. These subjects should enter the Taper Period.

#### Taper Period

The Taper Period (up to 4 weeks, depending on dose level achieved) will be required for subjects who complete the study or withdraw from treatment during the study if the following doses are achieved: LCM  $\geq 3$ mg/kg/day for subjects receiving oral solution, or LCM  $\geq 150$ mg/day for subjects taking tablets; lower doses will not require a taper. Taper of LCM may not be required for some subjects who complete the study or withdraw from the study prematurely, depending on the treatment option selected by the investigator in consultation with the subject and/or legal representative(s) or for subjects who participate in EP0151 or EP0152.

#### End of study and Safety Follow-up Period

Subjects who complete the study or withdraw prematurely from the study, and who discontinue use of LCM, should complete a Safety Follow-Up Visit 2 weeks ( $\pm 2$  days) after the last dose of LCM. A Safety Follow-Up Telephone Contact is required for all subjects (those who complete the study as planned or have withdrawn prematurely from the study). This telephone contact will occur 30 days (-1/+3 days) after the last dose of LCM. The Safety Follow-Up Visit and the Safety Follow-Up Telephone Contact are not required for subjects who participate in EP0151 or EP0152.

Unscheduled visits may be conducted at the discretion of the investigator.

The maximum duration of LCM administration during EP0034 will be approximately 2 years.

Detailed tabular schedules of study procedures and a study schematic diagram are included in Sections 5.2 and 5.3 of the protocol, respectively.

## **2.4 Determination of sample size**

Approximately 500 subjects from the SP0967 and the SP0969 study will be eligible to enroll in this open-label extension study. No formal hypothesis testing will be conducted in this study; therefore, no formal sample size calculations have been performed.

## 3 DATA ANALYSIS CONSIDERATIONS

### 3.1 General presentation of summaries and analyses

Statistical analysis and generation of tables, figures, subject data listings, and statistical output will be performed using SAS Version 9.1 or higher. All tables and listings will use Courier New font size 9.

Descriptive statistics will be displayed to provide an overview of the study results. For categorical parameters, the number and percentage of subjects in each category will be presented. The denominator for percentages will be based on the number of subjects appropriate for the purpose of analysis. Unless otherwise noted, all percentages will be displayed to 1 decimal place. No percentage will be displayed for zero counts, and no decimal will be presented when the percentage is 100%. For continuous parameters, descriptive statistics will include number of subjects (n), mean, standard deviation (SD), median, minimum, and maximum.

Decimal places for descriptive statistics will always apply the following rules:

- “n” will be an integer
- Mean, SD, and median will use 1 additional decimal place compared to the original data
- Minimum and maximum will have the same number of decimal places as the original value

All summaries, unless otherwise stated below, will be presented overall for all subjects and additionally based on the subject’s age at time of entry into study EP0034, using the following age groups:

- $\geq 1$  month to  $< 4$  years
- $\geq 4$  to  $< 18$  years

Summaries for PedsQL will be presented overall for all applicable subjects and additionally based on the subject’s age at Baseline (using the Baseline definition in [Section 3.3](#)), using the following age groups:

- $\geq 1$  month to  $\leq 12$  months
- $> 12$  months to  $\leq 24$  months
- $> 2$  years to  $\leq 4$  years
- $\geq 5$  to  $\leq 7$  years
- $\geq 8$  to  $\leq 12$  years
- $\geq 13$  to  $\leq 18$  years
- Total  $\geq 5$  years to  $\leq 18$  years

Summaries for CBCL/1½-5 will be presented overall for all applicable subjects and additionally based on the subject’s age at time of entry into study EP0034, using the following age groups:

- $\geq 18$  months to  $< 2$  years

- $\geq 2$  to  $< 4$  years
- Total  $< 4$  years
- $\geq 4$  to  $< 6$  years

Summaries for CBCL 6-18 will be presented overall for all applicable subjects and additionally based on the subject's age at time of entry into study EP0034, using the following age groups:

- $\geq 6$  to  $< 12$  years
- $\geq 12$  to  $< 16$  years
- Total  $\geq 6$  to  $< 16$  years
- $\geq 16$  years

Summaries for BRIEF-P will be presented overall for all applicable subjects and additionally based on the subject's age at time of entry into study EP0034, using the following age groups:

- $\geq 2$  to  $< 4$  years
- $\geq 4$  to  $< 5$  years

Summaries for BRIEF will be presented overall for all applicable subjects and additionally based on the subject's age at time of entry into study EP0034, using the following age groups:

- $\geq 5$  to  $< 12$  years
- $\geq 12$  to  $< 16$  years
- Total  $\geq 5$  to  $< 16$  years
- $\geq 16$  years

Summaries for Bayley-III assessments will be presented overall for all applicable subjects and additionally based on the subject's age at time of entry into study EP0034, using the following age groups:

- $\geq 1$  to  $< 6$  months
- $\geq 6$  months to  $< 1$  year
- $\geq 1$  year to  $< 18$  months

All summaries will be descriptive; no statistical hypothesis testing is planned.

A complete set of listings containing all documented data and all calculated data (eg, change from Baseline) will be generated, and will be sorted by site, subject number and visit (where applicable).

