1 SUMMARY

EP0034 is a Phase 3, multicenter, open-label, extension study to obtain long-term safety and efficacy data in pediatric subjects with epilepsy with partial-onset seizures treated with lacosamide (LCM) oral solution or LCM tablets as adjunctive therapy. The study will provide continued availability of LCM to subjects who have completed SP0969 (pediatric subjects with epilepsy aged ≥ 4 to < 17 years with partial-onset seizures). EP0034 will also be open to subjects who participate in SP0967 (pediatric subjects with epilepsy aged 1 month to < 4 years with partial-onset seizures). Both SP0969 and SP0967 are Phase 3, double-blind, placebo-controlled studies for LCM as adjunctive therapy.

Approximately 500 subjects from SP0967 and SP0969 may be eligible to enroll in this open-label extension study, for a maximum duration per subject of approximately 2 years. The number of sites is dependent on the number of enrolling centers from SP0967 and SP0969. The study will be conducted in North America, Europe, Latin America, and the Asia/Pacific regions, with the possibility to expand the study to other countries and regions if deemed necessary. At selected sites, subjects may also be able to participate in a substudy without withdrawing from EP0034.

The study medication is LCM in either the oral solution formulation or tablet formulation. Subjects may take either oral solution or tablets during the Treatment Period, based on clinical judgment, regardless of their weight. Lacosamide will be administered twice daily (bid) at approximately 12-hour intervals, once in the morning and once in the evening, in divided doses. The oral solution formulation will be measured and administered via a dosing syringe.

After completion of the Transition Period in the primary study, subjects will have been transitioned to a dose of LCM according to their weight. Subjects will receive LCM 10mg/kg/day (oral solution) for subjects weighing < 30 kg, LCM 6mg/kg/day (oral solution) for subjects weighing ≥ 30 kg to < 50 kg, and LCM 300mg/day (tablets) for subjects weighing ≥ 50 kg during at least their first week in the Treatment Period of EP0034. After 1 week in EP0034, the investigator may adjust the LCM dose during the Treatment Period based on clinical judgment within a range of 2mg/kg/day to 12mg/kg/day for the oral solution and 100mg/day to 600mg/day for the tablets.

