9.3 PedsQL

The PedsQL is a validated instrument that consists of generic core scales suitable for use with pediatric populations, including those with acute or chronic health conditions (Varni et al, 2001). The PedsQL will be administered according to the tabular schedules of study procedures (Section 5.2). The PedsQL will only be administered in countries where a validated translated version is available.

The PedsQL measurement model consists of developmentally appropriate forms for pediatric subjects 1 month to 12 months, 13 months to 24 months, 2 years to 4 years, 5 years to 7 years, 8 years to 12 years, and 13 years to 18 years of age. Self-report is measured for pediatric subjects ≥ 5 years to ≤ 18 years of age, and parent proxy report of child health-related quality of life (HRQoL) is measured for pediatric subjects ≤ 4 years of age. The PedsQL appropriate for each subject's age should be completed, with the following exception: If a subject ages up to the next form of the PedsQL within 1 year after the Baseline assessment of the primary study, the form that was used at the Baseline assessment should be completed for 1 year after the Baseline assessment, and subsequently the form consistent with his/her age at the time of assessment should be completed.

The multidimensional PedsQL generic core scales encompass the essential core domains for pediatric HRQoL measurement: Physical Functioning, Emotional Functioning, Social Functioning, and School Functioning. The PedsQL assessment is retrospective to the prior 4 weeks, and individual items are scored using a 5-point Likert scale (never, almost never, sometimes, often, or always). A total health summary score ranging between 0 and 100 is calculated from the sum of the raw scores, with higher scores indicating higher HRQoL.

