### 3.2.24 Age at time of visit/assessment

If date of birth is a complete date then age at the time of visit/assessment will be calculated as:

$$(\text{Date of visit} - \text{date of birth})/365.25$$

If date of birth is a partial date then age at the time of visit/assessment will be calculated as:

$$(\text{Enrollment age in years}) + [(\text{date of visit} - \text{informed consent date})/365.25]$$

This is converted to months by multiplying by 12 if required.

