#### **9.2.3.2 Pediatric Quality of Life Inventory Ages $> 2$ years**

The multidimensional PedsQL  $> 2$  years generic core scales encompass the following core domains for pediatric HRQoL measurement: Physical Functioning, Emotional Functioning, Social Functioning, and School Functioning.

Calculated values and changes from Baseline for the total scale score (all items), the psychosocial health summary score, the physical health summary score and each of the 4 scale scores will be summarized for each visit and for Last Visit. This will be repeated by enrollment group. For subjects 5 years and older at Baseline, changes from Baseline will be calculated for all visits, even when the questionnaire version used is different from the one at Baseline. For subjects less than 5 years at baseline, the change from Baseline will be calculated only when the same questionnaire version is used at Baseline and post-Baseline. All PedsQL  $> 2$  years data will be listed.

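### The PedsQL age bands in SAP 3.1 cover every child neither on decimal age nor on completed years, and age at Baseline is not defined; only descriptive age-group rows are affected

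*SAP*

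**What the plan says.** SAP 3.1: "Summaries for PedsQL will be presented overall for all applicable subjects and additionally based on the" subject's age at Baseline. The listed groups are ≥1 to ≤12 months, >12 to ≤24 months, >2 to ≤4 years, ≥5 to ≤7, ≥8 to ≤12, ≥13 to ≤18, and Total ≥5 to ≤18 years.

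Protocol 9.3 labels the forms by whole years, for example "2 years to 4 years, 5 years to 7 years", with parent proxy report up to age 4 and self-report from age 5.

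No section defines age at Baseline. SAP 3.3 defines Baseline values only. The nearby age rules are:
- SAP 3.2.9, age at EP0034 entry: an unspecified SDTM derivation when the birth date is complete, otherwise earlier age plus calendar months divided by 12.
- SAP 3.2.24: "If date of birth is a complete date then age at the time of visit/assessment will be calculated as" days since birth divided by 365.25.

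SAP 9.2.3.2 splits the change-from-Baseline rule at exactly 5 years: "For subjects less than 5 years at baseline, the change from Baseline will be calculated only when the same questionnaire version is used" at both time points, while for children of 5 and older versions may be mixed.

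Also in SAP 3.1, CBCL/1½-5, CBCL/6-18, BRIEF-P and BRIEF are banded by age at entry into EP0034. Protocol 10.8.7 and 10.8.8 assign the form by age at assessment, except that the younger form is kept for 1 year after the primary-study Baseline.

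**The concern.** Bounds that suit form labels in whole years are being used as analysis cuts. A child of 4.5 years completes the 2-to-4-year proxy form, yet is above 4 and below 5. Ages 7.5 and 12.5 fail in the same way. If the tables are programmed as printed, year-groups drop out of the age-group rows without any message.

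The other groupings in SAP 3.1 use contiguous ≥ and < bounds, and SAP Amendment 3 (section 13.3, Change #6) moved the second infant PedsQL band from ≥13 months to >12 months. The years bands therefore look like an oversight.

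At stake is quality of life by age group, under one of the study's other objectives. The 4-year-olds matter most: on decimal age their proxy reports would appear only in summaries that also contain self-reports.

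**Working it through.** The plan states no figure to reproduce. The check places each age in the printed PedsQL bands.

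**Inputs.** Bands: SAP 3.1. SP0969 ages: ≥4 to <17 years, a 13-year span (Protocol section 1). SP0967 ages: 1 month to <4 years, a span of 48 − 1 = 47 months (Protocol section 1). The age distribution is not given, so uniform ages are an assumption and other shapes give a range.

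**Decimal age, SP0969.** Uncovered intervals: 4 to 5, 7 to 8, 12 to 13 (open at both ends).
- In no individual band, uniform: 3/13 = 23.1%.
- In no listed group: Total ≥5 to ≤18 takes in the second and third intervals, leaving 1/13 = 7.7%.
- Age in completed months divided by 12: 11 months are lost per gap, so 33/156 = 21.2% and 11/156 = 7.1%.

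Other shapes on 4 to 17:

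| Shape | No individual band | No listed group |
|---|---|---|
| Density rising linearly from 4 | (0.5 + 3.5 + 8.5)/84.5 = 14.8% | 0.5/84.5 = 0.6% |
| Density falling linearly to 17 | (12.5 + 9.5 + 4.5)/84.5 = 31.4% | 12.5/84.5 = 14.8% |
| Truncated normal, mean 14, SD 2 | 16.2% | 0.0% |
| Truncated normal, mean 10, SD 3.5 | 22.5% | 3.6% |
| Truncated normal, mean 6, SD 2 | 35.8% | 17.8% |

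**Completed years.** Ages 4 to 16 all fall in a band, so 0/13 of SP0969 is lost. A child of 30 months, however, is 2 in completed years. That is not >2, and the child is past the ≤24-month band. If ages are uniform, this affects completed months 25 to 35, or 11/47 = 23% of the SP0967 range (12/47 = 26% counting the whole interval from 24 to 36 months).

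**CBCL and BRIEF.** Week 96 is 672/365.25 = 1.84 years after entry, so the 1-year hold has ended.
- Aged 4 at entry: at least 5.84 at Week 96, so BRIEF applies. BRIEF bands start at 5 at entry.
- Aged 5 at entry: at least 6.84, so CBCL/6-18 applies. Its bands start at 6 at entry.
- Turned 5 before entry but still held on BRIEF-P: the top BRIEF-P band is <5.

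None of these children has a band in the table for that form, whichever age convention is used.

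**The case against.** The strongest reply has four parts.

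- **The Total row.** A reader might infer that a fifth or more of SP0969 children fall in no age group at all. The documents do not support that: Total ≥5 to ≤18 years takes in the children between 7 and 8 and between 12 and 13, so only those between 4 and 5 are in no listed group. This stands.
- **Decimal age is not prescribed here.** SAP 3.2.24 is invoked for laboratory, vital-sign and ECG criteria, not for PedsQL, and the form labels suggest completed years. On that reading no SP0969 child is lost. This stands too, so the 23% depends on an age rule and an age distribution that the documents do not give.
- **A sensible programmer would take >2 years as more than 24 months and the upper limits as completed years.** That hybrid does cover everyone. But it applies two conventions to the two ends of one band, and the SAP does not state it.
- **Little is lost.** All children stay in the overall summary, the repeat by enrollment group and the listings. SAP 9.2.3.1 and 9.2.3.2 already separate the infant forms from the older ones, and the rule at 5 years has no gap. A child who moves to BRIEF or CBCL/6-18 without a Baseline on that form is not in the change or shift summaries anyway, so the CBCL and BRIEF mismatch touches mainly observed scores. This limits the importance but does not make the bands right.

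**Conclusion.** The bounds are faulty as printed, and the age variable they apply to is undefined. Without an unstated mixed reading, some children match no individual PedsQL band. The size turns on the convention: 23% of SP0969 with decimal and uniform ages (about 15% to 36% over the shapes tried), of whom about 8 percentage points (about 0 to 18) are in no listed group; none of SP0969 with completed years, when the loss moves to two-year-olds in SP0967. The CBCL and BRIEF mismatch holds under either convention; how many children it affects cannot be computed from the documents.

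A reader might go on to infer that children are excluded from the quality-of-life analysis or that the change-from-Baseline rule is broken; neither follows. The consequences are confined to descriptive age-group rows, with no hypothesis test and no primary or secondary variable involved. It should be corrected because the printed rule can remove children from rows without notice and the correction is simple.

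**What to change.** In SAP 3.1, do one of the following for PedsQL:
- group by the form completed at Baseline, which is the cleaner option; or
- define age at Baseline and use contiguous cuts that keep the present infant boundaries: ≥1 to ≤12 months, >12 to ≤24 months, >24 months to <5 years, ≥5 to <8, ≥8 to <13, ≥13 years, and Total ≥5 years.

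With contiguous cuts, 0% of SP0969 children are left out. The infant limits need no change; shifting them to 13 and 25 months would reclassify children for no gain.

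In the same section, set the CBCL/1½-5, CBCL/6-18, BRIEF-P and BRIEF bands so that every child who completes a form has a band in that form's table, for example by using age at assessment or by opening the lowest and highest bands.

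The cost is SAP wording and the matching table shells. No new data are needed.
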